- For a 28-day cycle: maximum of 13 cycles

Reference Therapy, Dosage, and Mode of Administration: Not applicable

Study Schedule/Procedures:

Subjects will have regularly scheduled study visits at the clinical site on Day 1 of each cycle. Additional study visits may be required during some cycles to monitor for safety, efficacy, or for PK [REDACTED] evaluations. Study visits are as follows:

- **Screening:** up to 28 days before enrollment. Screening will begin at the time that the subject signs the informed consent and will continue until the date the subject is enrolled in the study (Cycle 1 Day 1).

- **Cycle 1 and Cycle 6:** Day 1, Day 2, and Day 7 (± 1 day).
- **Cycle 2:** Day 1 (± 1 day) and Day 7 (± 1 day).
- **All other treatment cycles:** Day 1 (± 3 days).
- **Efficacy assessments:** Every 8 weeks (± 7 days) for 12 months, and then every 12 weeks (± 7 days) thereafter until disease progression is determined.
- **End of treatment:** ± 3 days.
- **Safety follow-up:** 30 days (+ 7 days) and 60 days (+ 7 days) after end of treatment.

Safety Assessments:

Subjects will have regularly scheduled study visits at the clinical site on Day 1 of every cycle where targeted physical examinations, vital sign collection, ECOG performance status, collection of concomitant medications, and AE assessments will be performed. A 12-lead ECG will be performed at screening, Cycle 1 Day 1, Cycle 2 Day 1, and then Day 1 of **every other cycle** after Cycle 2 (eg, Cycle 4, Cycle 6, Cycle 8). Triplicate ECG measurements will be performed at Screening, Cycle 1 Day 1, and Cycle 6 Day 1, in conjunction with PK assessments. Laboratory assessments will be collected on Day 1 of each cycle, with more frequent blood sample collection during the first and second cycles (Day 1 and Day 7) to evaluate for DLTs. Toxicities will be monitored continuously and will be graded using the NCI CTCAE v4.03 criteria.

On Day 1 of the first 4 cycles (Cycle 1 Day 1, Cycle 2 Day 1, Cycle 3 Day 1, and Cycle 4 Day 1), subjects will be required to stay at the study site for at least 4 hours after infusion of study drug for safety observation. It is recommended that the subject does not leave the site for any reason during the safety observation period. During the safety observation period, subjects will be assessed for the onset of acute AEs.

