^c On Day 1 of the first 4 cycles (C1D1, C2D1, C3D1, and C4D1), subjects will be required to stay at the study site for safety observation for up to 4 hours postinfusion. It is recommended that the subject does not leave the site for any reason during the safety observation period. During the safety observation period, vital signs (blood pressure, pulse, respiratory rate, and body temperature) will be assessed every 60 minutes ± 10 minutes (eg, 1 hour postinfusion, 2 hours postinfusion, 3 hours postinfusion, etc). Subjects will also be assessed for the onset of acute AEs.

- ^d Laboratory assessments may also be required on additional visit days as described in [Table 8](#) and [Table 9](#).
- ^e All 12-lead ECGs will be performed with the subject in a recumbent or semirecumbent position after 5 minutes of rest and should not be performed within 15 minutes after a blood collection.
- ^f In the event that a single QTc is > 470 milliseconds, the subject may enroll if the average QTc for the 3 ECGs is < 470 milliseconds or with approval from the medical monitor.
- ^g **Triplicate ECG measurements are required at screening, C1D1 (in conjunction with PK samples), and C6D1 (in conjunction with PK samples).** Subsequent ECGs only need to be performed in triplicate if there has been a QT prolongation on study or if the ECG shows a clinically significant abnormality not present at baseline. See [Table 11](#) for information regarding timing of triplicate ECGs.
- ^h A 12-lead ECG should be performed on Day 1 of every other cycle after Cycle 2 (eg, Cycle 4, Cycle 6, Cycle 8, Cycle 10).
- ⁱ The initial tumor imaging will be performed within 28 days before the first dose of study drug. Scans performed as part of routine clinical management are acceptable for use as the screening scan if they are of diagnostic quality and performed within 28 days before the first dose of study drug. The same imaging technique should be used for a subject throughout the study. Local reading (investigator assessment with site radiology reading) will be used to determine eligibility and for subject management.

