7.6.4. Electrocardiograms

All 12-lead ECGs will be performed with the subject in a recumbent or semirecumbent position after 5 minutes of rest and should not be performed within 15 minutes of a blood collection. All 12-lead ECGs will be acquired using an ECG analysis system with analysis and printing capabilities, as well as digital transmission capabilities to a central capture module at the central ECG laboratory.

Timed triplicate ECGs (separated by 5 minutes) will be conducted at screening and in conjunction with the pre- and postinfusion PK timepoints on C1D1 and C6D1 (see [Table 11](#)). The specified postdose timepoint may be adjusted based on emerging PK data.

A 12-lead ECG should be performed on Day 1 of every other cycle after Cycle 2 (eg, Cycle 4, Cycle 6, Cycle 8, Cycle 10, etc). Subsequent ECGs only need to be performed in triplicate if there has been a QT prolongation on study or the ECG shows a clinically significant abnormality not present at baseline.

The automated 12-lead ECGs readings will be interpreted by the investigator, or qualified designee at the site to be used for immediate subject management. The decision to include or exclude a subject or withdraw a subject from the study based on a centrally analyzed ECG flagged as "Abnormal, Clinically Significant" is the responsibility of the investigator, in consultation with the medical monitor, as appropriate. Clinically significant abnormal findings before signing consent should be recorded as medical history. Clinically significant abnormal findings after signing consent should be recorded as an AE. In the event that a single QTc is $>$ 470 milliseconds at screening, the subject may enroll if the average QTc for the 3 ECGs is $<$ 470 milliseconds or with approval from the medical monitor. For subjects with an intraventricular conduction delay (QRS interval $>$ 120 milliseconds) at screening, the JTc

interval may be used in place of the QTc with sponsor approval. In addition, the JTc interval should be used for all subsequent assessments.

Table 11: Timing of Triplicate Electrocardiograms

Study Visit	Timing of Sample			
	Any Time	Preinfusion	Postinfusion PK Timepoint	4-Hr Postinfusion PK Timepoint
Screening	X			
C1D1		X ^a	X ^b	X ^a
C6D1		X ^a	X ^b	X ^a

^a Electrocardiograms should be conducted before but within 30 minutes of the PK blood draw at the corresponding timepoint.

^b Electrocardiograms should be performed 15 to 30 minutes after the corresponding PK sample is drawn.

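### The stay after infusion on Day 1 of Cycles 1 to 4 is a 4-hour minimum in the protocol synopsis but a 4-hour maximum in Table 7, Section 6.2 and Section 7.6.3

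*Protocol*

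**What the plan says.** Four places in the current protocol set the observation period after infusion on Day 1 of Cycles 1 to 4.

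- Synopsis, Safety Assessments: "subjects will be required to stay at the study site for at least 4 hours after infusion". What is required during that time is stated as "During the safety observation period, subjects will be assessed for the onset of acute AEs".
- Table 7 footnote c, Section 6.2 and Section 7.6.3: "subjects will be required to stay at the study site for safety observation for up to 4 hours postinfusion".

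Table 7 footnote c and Section 7.6.3 add vital signs, which "will be assessed every 60 minutes ± 10 minutes" during the observation period, with the examples "1 hour postinfusion, 2 hours postinfusion, 3 hours postinfusion, etc". Section 6.2 and the synopsis do not give this hourly schedule. All four places recommend that the subject not leave the site while under observation. The SAP does not mention the period.

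**The concern.** The same rule is written once as a minimum and three times as a maximum. A site that follows the schedule of assessments or the body sections could discharge a subject before 4 hours in good faith and so breach the synopsis. A monitor could not say consistently whether a 3-hour stay is a protocol deviation.

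The rule matters because this is dose escalation of an immune agonist antibody. The starting dose rests on in vitro and monkey data (Section 1.3.1), and Section 1.2.3 acknowledges that monkeys may not fully reproduce the human immune response. The event left exposed is a reaction that begins after an early discharge but before 4 hours.

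**Working it through.** The protocol gives no figure to reproduce here. The check is whether the two wordings can both hold, and whether some other procedure keeps the subject on site anyway.

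**1. Compatibility.** Let T be the length of stay after infusion. The synopsis requires T ≥ 4 h; the three body locations, read literally, allow T ≤ 4 h. Only T = 4 h meets all four. A stay of 3 h falls within the body wording's limit and breaches the synopsis.

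**2. Visits covered.** C1D1, C2D1, C3D1 and C4D1: four per subject who reaches Cycle 4.

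**3. Cycle 1 Day 1.** Table 13 (Section 7.8.1) schedules a PK sample at 4 h ± 30 min after infusion, so the draw may fall between 3.5 h and 4.5 h. Section 7.6.4 ties triplicate ECGs to the "pre- and postinfusion PK timepoints on C1D1 and C6D1". For the 4-hour timepoint, Table 11 footnote a says "Electrocardiograms should be conducted before but within 30 minutes of the PK blood draw at the corresponding timepoint", so the blood draw is the later of the two procedures.

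- Earliest compliant draw: 240 − 30 = 210 min (3.5 h).
- Largest shortfall against the synopsis: 240 − 210 = 30 min.
- A draw at or after the nominal time leaves no shortfall.

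**4. Day 1 of Cycles 2, 3 and 4.**

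- PK: Table 13 shows only preinfusion samples on these days.
- Triplicate ECGs: Table 11 places postinfusion recordings only on C1D1 and C6D1.
- Other ECGs: the synopsis says "A 12-lead ECG will be performed at screening, Cycle 1 Day 1, Cycle 2 Day 1", then every other cycle, which brings in C4D1. No time after infusion is given for C2D1 or C4D1.
- Vital signs: these are hourly within the observation period, so they take their end from that period and cannot define it. The examples stop at 3 hours with an open-ended continuation.

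No readable procedure therefore fixes a 4-hour stay on these days. Visits affected per subject: 4 − 1 = 3 at most, fewer if the subject stops before Cycle 4.

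**5. Limits of the check.** Tables 9 and 13 are partly redacted, and Section 7.9, which Section 6.2 also cites for sampling, is not readable. A redacted sample could hold subjects on one or more of these days, so three is an upper bound. The documents give no basis for estimating how many stays would be cut short.

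**The case against.** The strongest reply is that the body wording is loose drafting for a 4-hour stay. It makes staying on site a requirement, and the hourly vital signs, illustrated at 1, 2 and 3 hours and then continuing, point to a fourth set. A site that discharged at 1 or 2 hours would not be following the schedule as illustrated. This stands as evidence of intent. It does not settle the rule, because the times are examples and apply only while the observation period lasts.

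A second reply is that nothing gives the synopsis precedence. Three locations agree with each other and the synopsis is the outlier, so a change to one synopsis phrase would also remove the conflict. That is true. The reason to prefer the minimum is that it is the more protective reading and is already stated as a requirement.

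Third, the consequence is small and conjectural. Section 5.4.8 says infusion reactions tend to appear during the infusion or soon afterwards, and Table 6 calls for closer vital-sign monitoring once one occurs. This also stands, and it is why the point is rated minor.

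**Conclusion.** The inconsistency is real: four current, unredacted statements of one safety rule disagree on whether 4 hours is the least or the most a subject must stay. The size is limited. On C1D1 the possible shortfall is at most 30 minutes, and on C2D1, C3D1 and C4D1 the stay has no fixed length. The count of up to three visits per subject assumes that no redacted procedure holds the subject on those days. The likely intent, a 4-hour stay, is clear and satisfies all four statements, so what needs correcting is the wording. Sample size, error rates, escalation rules and planned analyses are unaffected.

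**What to change.** In Table 7 footnote c, Section 6.2 and Section 7.6.3, replace the upper limit with a minimum of 4 hours after infusion, matching the synopsis. In Table 7 footnote c and Section 7.6.3, list vital signs at 1, 2, 3 and 4 hours after infusion, each ± 10 minutes, in place of the open-ended examples.

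The cost is wording in three places, in a protocol clarification or the next amendment. The synopsis already requires the 4-hour stay, so that part adds no burden. The explicit 4-hour vital-sign set is a small addition to the synopsis, which asks only for acute AE assessment during observation, although the body's hourly schedule implies that set over a 4-hour stay. If the sponsor regards either change as a change of procedure, Section 10.1 requires sponsor and then IRB/IEC approval, so it would best go with the next amendment.

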HBV	hepatitis B virus
HCV	hepatitis C virus
HIPAA	Health Insurance Portability and Accountability Act of 1996
HIV	human immunodeficiency virus
ICF	informed consent form
ICH	International Conference on Harmonisation
IEC	independent ethics committee
IgG1	immunoglobulin G1
IL	interleukin
IN	Investigator Notification
INR	international normalized ratio
irAE	immune-related adverse event
IRB	institutional review board
IV	intravenous
IWRS	Interactive Web Response System
LTBR	lymphotoxin beta receptor
mAb	monoclonal antibody
MABEL	minimum anticipated biological effect level
MedDRA	Medical Dictionary for Regulatory Activities
MNTD	maximum number of tolerated doses
mRECIST	modified Response Evaluation Criteria in Solid Tumors
MRI	magnetic resonance imaging
MSI	microsatellite instability
MTD	maximum tolerated dose
NF κ B	nuclear factor kappa-light-chain-enhancer of activated B cells
NOEL	no-observed-effect level
NSCLC	non-small cell lung cancer
PAD	pharmacologically active dose
PBMC	peripheral blood mononuclear cells
█	██████████

Abbreviation	Definition
PD1	programmed cell death protein 1
PFS	progression-free survival
PK	pharmacokinetic
PR	partial response
PT	prothrombin time
RCC	renal cell carcinoma
RECIST	Response Evaluation Criteria in Solid Tumors
NSAID	nonsteroidal anti-inflammatory drug
RNA	ribonucleic acid
RP2D	recommended Part 2 dose
SAE	serious adverse event
SD	stable disease
SSD	safe starting dose
SUSAR	suspected unexpected serious adverse reaction
TCR	T-cell receptor
TNF	tumor necrosis factor
TNFR	tumor necrosis factor receptor
TNFRSF	tumor necrosis factor receptor super family
TNFSF	tumor necrosis factor super family
Treg	regulatory T cell
TWEAK	tumor necrosis factor–related weak inducer of apoptosis
ULN	upper limit of normal

1. INTRODUCTION

This is a Phase 1/2, multicenter, open-label, dose-escalation study. The study will be conducted in 2 parts. Part 1 will utilize a 3 + 3 design to determine the maximum tolerated dose (MTD) or pharmacologically active dose (PAD) for INCAGN01876 in subjects with advanced or metastatic solid tumors. Part 2 of the study will further evaluate the safety, tolerability, preliminary efficacy, pharmacokinetics (PK), [REDACTED] of the recommended Part 2 dose (RP2D) and schedule of INCAGN01876 in subjects with advanced or metastatic adenocarcinoma of the endometrium, melanoma, non-small cell lung cancer (NSCLC), and renal cell carcinoma (RCC).

1.1. Background

1.1.1. The Role of the Immune System in Cancer

The immune system is comprised of diverse sets of cells designed to protect a host from pathogens while distinguishing from host and foreign antigens. This immune response is controlled by a series of checks and balances to allow for robust immune responses to pathogens while preventing either an excessive inflammatory event or an autoimmune response. Through immune surveillance, the immune system has been shown to recognize, attack, and destroy tumor cells (Wolchok and Saenger 2008). The presence of tumor-infiltrating lymphocytes in cancer tissue among various malignancies has been shown to confer a more favorable prognosis (Mei et al 2014, Salgado et al 2015, Gooden et al 2011, Schreiber et al 2011, Bremnes et al 2011, Talmadge 2011, Shirabe et al 2010, Noshio et al 2010, Bellati et al 2009, Oble et al 2009, Uppaluri et al 2008). [REDACTED]

[REDACTED] (Noshio et al 2010, Chang et al 2014, Preston et al 2013, Yoon et al 2012, Kim et al 2013, Mathai et al 2012, Liu et al 2011, Kirk 2010). Although the immune system has been shown to recognize and reject a tumor, many tumors evade immune surveillance or develop mechanisms of resistance.

Histologic evaluation of multiple human cancers show extensive infiltration by inflammatory and immune cells (Galon et al 2006), suggesting that the immune system responds less effectively to malignancy. As tumors grow, an "equilibrium" is reached where tumor growth is matched by immune-mediated tumor destruction. Eventually, malignant cells either accumulate mutations, making them nonimmunogenic, or immunosuppressive pathways become activated, allowing the tumor to escape immune recognition (DuPage et al 2012, Schreiber et al 2011, Dunn et al 2002, Matsushita et al 2012). The accumulation of suppressive cells and an inhibitory cytokine milieu in and around a tumor can form an immunosuppressive environment that prevents successful T-cell-mediated destruction of malignant cells (Schaer et al 2011). Overcoming tumor resistance to immune surveillance either through stimulating the immune response or preventing inhibition is the basic rationale for the development of immunotherapies.

Targeting the immune system is a proven and effective approach for cancer therapies. Food and Drug Administration-approved checkpoint inhibitors, such as ipilimumab, nivolumab, and pembrolizumab, allow for the immune response to continue to proliferate in spite of inhibitory

signals. The activation of costimulatory pathways through the glucocorticoid-induced tumor necrosis factor receptor (GITR) is another promising treatment approach and is the focus of this clinical trial.

1.1.2. Immune Modulators

Immune cell receptors known as checkpoint modulators (collectively known as immune modulators) provide a critical mechanism for the regulation of an immune response. Checkpoint modulation can either diminish an inflammatory process or escalate an immune response. Modulation of coinhibitory and costimulatory receptors of the immune system has become a proven approach for the immunotherapy of cancer (Chen and Mellman 2013).

The development of fully human antibodies that target and modulate immune receptors in humans have led to the discovery of multiple validated targets for the immunotherapy of cancer (Chen and Mellman 2013, Leach et al 1996). Antibodies that engage the various checkpoint modulators can broadly be classified into 2 categories based on mechanism of action: antagonists (blocking the interaction between receptor and cognate ligand[s]), and agonists (inducing or facilitating receptor-forward signaling). Clinical testing of therapeutic antibodies has demonstrated their ability to influence the direction and magnitude of the immune responses, leading to tumor eradication (Yao et al 2013). The blocking of coinhibitory receptors such as cytotoxic T-lymphocyte-associated protein 4 (CTLA-4) or programmed cell death protein 1 (PD1) blockade are the basis of FDA-approved therapies to augment an antitumor immune response. Clinical and preclinical research has demonstrated a rationale for targeting costimulatory receptors within the tumor necrosis factor super family (TNFSF; Schaer et al 2013).

1.1.3. Glucocorticoid-Induced Tumor Necrosis Factor Receptor and the Tumor Necrosis Factor Super Family

GITR belongs to the TNFSF, and is activated by its cognate ligand, GITRL. GITR regulates a variety of immune cell functions including T-cell proliferation, differentiation, cytokine production, and survival (Smith et al 1994). GITR expression is generally restricted to normal tissues with high immune cell composition, including the peripheral blood, bone marrow, spleen, and thymus (Gurney et al 1999). GITR is expressed on some regulatory T cells (Tregs), is upregulated upon T-cell activation of both CD4+ and CD8+ T cells, and is a costimulator in the activation of these T cells (Allan et al 2007, Bianchini et al 2011, Schaer et al 2012).

In mice, the GITR-GITRL system is implicated in development of autoimmune and inflammatory responses, as well as promoting protective immunity to pathogens and tumors (Nocentini et al 2012). Animals treated with a GITR-Fc fusion protein leading to an attenuated GITR signaling showed signs of ameliorated autoimmunity. By contrast, an agonist anti-GITR antibody augmented an immune response to viral, bacterial, and parasitic infections. Unlike murine models, the cell surface expression of GITR is undetectable on the majority of human peripheral blood immune cell populations.

(Schaer et al 2012, Ronchetti et al 2015).

1.1.4. Glucocorticoid-Induced Tumor Necrosis Factor Receptor and Activated T Cells

During T-cell priming, peptide-loaded major histocompatibility complex molecules expressed by antigen-presenting cells are recognized by T cells through the T-cell receptor (TCR; [Wilson and Villadangos 2005](#)). Signaling through the TCR leads to rapid GITR upregulation on human T cells ([Ronchetti et al 2015](#)). In the context of major histocompatibility complex–mediated TCR activation, the GITR pathway provides an important costimulatory signal leading to enhanced T-cell proliferation and survival and cytokine function ([Tone et al 2003](#)). These outcomes are mediated by signaling *via* the nuclear factor κ -light-chain-enhancer of activated B cells (NF κ B) pathway, which can promote T-cell survival in response to weak, rather than strong TCR signals ([Zhan et al 2008](#), [Gerondakis et al 2014](#)). In addition to the costimulatory function of the GITR pathway within the antigen-presenting cell T-cell synapse, GITRL/GITR interactions on endothelial cells may also contribute to leukocyte adhesion and transmigration at sites of infection or into tumors ([Lacal et al 2013](#)). Modulation of the GITR costimulatory pathway may therefore provide a therapeutically tractable strategy for increasing T-cell responsiveness against relatively weak antigens, such as those expressed by tumor cells. This possibility is further supported by the observation that ectopic expression of GITRL on tumor cells results in rapid tumor regression following a period of transient growth ([Piao et al 2009](#)). In this example, antitumor efficacy was mediated by enhanced T-cell function, a finding that established a link between tumor regression and GITR-dependent T-cell costimulation within the tumor microenvironment. Modulation of GITR signaling in T cells using a murine mAb GITR agonist, DTA-1, has similarly been shown to enhance T-cell–mediated immune responses, leading to convincing single-agent antitumor activity in a range of syngeneic mouse tumor models ([Turk et al 2004](#), [Ko et al 2005](#)).

1.1.5. Glucocorticoid-Induced Tumor Necrosis Factor Receptor and T Regulatory Cells

GITR expression has been observed on Tregs within the tumor microenvironment, which may play a role in suppressing an antitumor immune response ([Wing et al 2008](#), [Zou et al 2006](#)). Preclinical work with a mAb directed at GITR have been shown to deplete Tregs through 2 mechanisms: 1) T-cell lineage changes and 2) through antibody-dependent cell-mediated cytotoxicity (ADCC). This has been observed with DTA-1, which demonstrated that agonistic engagement with the GITRL on Tregs leads to lineage instability and conversion to nonregulatory T cells ([Schaer et al 2013](#)). In addition, GITR has shown significant antitumoral effects by depleting Tregs via Fc γ receptor (Fc γ R)–mediated antibody-dependent cell-mediated phagocytosis (ADCP; [Bulliard et al 2013](#)). This has been observed in murine models with DTA-1, in which a single dose of DTA-1 resulted in rapid and selective elimination of most Treg cells within the tumor microenvironment ([Bulliard et al 2013](#)). It was confirmed that Treg depletion is required for optimal DTA-1–dependent antitumor activity, and the intratumoral Treg depletion is consistent with involvement of the immune effector cell mechanisms, such as ADCC and/or ADCP of the antibody labeled target cell. Together, these 2 mechanisms have been shown to deplete Tregs in the tumor microenvironment and ultimately confer a modest delay in tumor growth ([Kim et al 2015](#)).

